6.2. Secondary Endpoint(s)

Quantification of the expression and distribution of mini-dystrophin detected by LC-MS and the immunofluorescence assay can provide evidence of expression of the transgene product. To limit possible variability by averaging or comparing results from different sections of a given muscle biopsy tissue, only sectioned tissue with results from each of the planned assays will be included in the summary.

The bootstrapping method (Efron 1979²) will be used to compute the 95% CIs of the parameters of interest for robust evaluation without underlying distributional assumptions.

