2.3. Secondary Estimand(s)

Analyses of the secondary endpoints by population (ambulatory, non-ambulatory, overall) and by dose cohort are described in Section 6.2. For each secondary endpoint, the four attributes associated with the estimand are summarized below.

- Population: Among ambulatory and non-ambulatory participants who meet the inclusion and exclusion criteria, those who receive a single IV infusion of fordadistrogene movaparvovec.
- Variable: Secondary endpoints listed in Section 2.1.

- Intervention effect: Effect of treatment on dystrophin/mini-dystrophin expression and distribution through 1 year post-treatment, regardless of adherence to background and protocol-mandated glucocorticoid regimens.
- Population-level summary: Changes from Baseline (pre- and post-) for treatment difference through 1 year post-treatment

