3.2.1.1. Mini-dystrophin expression

Dystrophin and mini-dystrophin expression levels will be measured by LC-MS assay. For the LC-MS assay, there are two reportable peptides:

- 1. LEMPSSLMLEVPTHR (LEMP) peptide results will quantify the mini-dystrophin transgene protein levels following treatment with fordadistrogene movaparvovec.
 - No mini-dystrophin transgene protein will be expressed in the tissue samples obtained prior to the administration of fordadistrogene movaparvovec.
- 2. LLQVAVEDR (LLQV) peptide results will quantify the total dystrophin protein including both full-length, endogenous dystrophin protein and the mini-dystrophin transgene protein.

Revertant endogenous fibers usually exist due to a mechanism that restores the reading frame (Klein et al., 1992¹). Dystrophin levels from revertant fibers may be measurable by LC-MS assay. Baseline is defined as the endogenous dystrophin levels reflected in the tissue sample collected prior to the administration of fordadistrogene movaparvovec.

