3.2.1.2. Mini-dystrophin distribution

Muscle fibers expressing both endogenous dystrophin protein and mini-dystrophin transgene protein will be identified by positive staining. Percentage of positive muscle fibers will be calculated for each muscle biopsy.

Dystrophin distribution will be evaluated by immunofluorescent staining using two antibodies.

1. DYSB antibody that recognizes both endogenous dystrophin protein and minidystrophin transgene protein from the pre-dose tissue biopsy for the endogenous dystrophin antibody.

For the baseline assessment, the distribution of the fiber MSD for each individual fiber will be evaluated for each participant to assess the expression level of total dystrophin protein. Baseline will be derived from the fiber MSD for each individual fiber in the tissue biopsies that were obtained prior to the administration of fordadistrogene movaparvovec.

2. Mini-dystrophin specific antibody that only recognizes the mini-dystrophin transgene protein

No mini-dystrophin transgene protein fibers will be contained in the tissue samples obtained prior to the administration of fordadistrogene movaparvovec.

The positive threshold value for the mini-dystrophin specific antibody represents a pooled average MFI value from 19 ambulatory baseline, pretreatment biopsies.

[figure not shown]
For the determination of percent of positive muscle fibers and the derivation of the baseline value, refer to Section 6.2.2 for details.

[figure not shown]

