4. ANALYSIS SETS (POPULATIONS FOR ANALYSIS)

Data for all participants will be assessed to determine if the participants meet the criteria for inclusion in each analysis population prior to releasing the database.

For purposes of analysis, the following populations are defined:

Population	Description	
Enrolled	All subjects who sign the informed consent document.	
FAS	All enrolled participants who receive fordadistrogene	
	movaparvovec. Analyses will be performed on the FAS	
	population unless otherwise specified.	
Safety	All enrolled participants who receive fordadistrogene	
	movaparvovec. Participants will be analyzed according to	
	intervention they actually received.	
Pharmacodynamic	All participants in the FAS who have baseline and at least	
Analysis Set	one post-dose mini-dystrophin parameters of interest reported.	

Population	Description
Ambulatory	All participants in the FAS who meet the study eligibility
	criteria for ambulatory status at enrollment: able to walk 10
	meters unassisted and rise from floor within seven seconds.
Non-ambulatory	All participants in the FAS who meet the study eligibility
	criteria for non-ambulatory status at enrollment: unable to walk
	10 meters unassisted.
Low dose cohort	All participants in the FAS who receive 1E14 vg/kg per the
	ITR-based method.
High dose cohort	All participants in the FAS who receive 3E14 vg/kg per the
	ITR-based method or 2E14 vg/kg per the TG-based titer
	method.
CCI	
Non-sirolimus cohort	All participants in the FAS who do not receive sirolimus within
	2 weeks before and after fordadistrogene movaparvovec
	infusion.
Regardless of adherence to	All participants in the FAS, regardless of adherence to
glucocorticoid regimen	background or protocol-mandated glucocorticoid regimens.

The term "ambulatory status at baseline" will be used to describe the stratification factor (ambulatory versus non-ambulatory) used to partition the study participants and report the corresponding group results. The term "overall" will be used to refer to all participants in the FAS.

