6.2.1. Mini-dystrophin/Dystrophin Expression by LC-MS

Endpoints:

- Mini-dystrophin levels, expressed as fmol/mg of total protein, measured by LC-MS assay, LEMPSSLMLEVPTHR (LEMP) peptide
- Total dystrophin levels, expressed as fmol/mg of total protein, measured by LC-MS assay, LLQVAVEDR (LLQV) peptide
- Total dystrophin levels, expressed as percent normal, measured by LC-MS assay, LLQVAVEDR (LLQV) peptide

The analyses listed below will be performed for each of the 3 endpoints. The method for handling results below the LLOQ is described in Section 5.3.3. The analyses will be performed using the Pharmacodynamic Analysis Set. Presentations will include:

- Raw values, change from baseline and % change from baseline will be summarized descriptively by dose cohort, ambulatory status at baseline, and study visit.
- A boxplot (for cohort(s) with over 3 participants, data points display only for cohort with ≤3 participants) presenting the distribution of the change from baseline against study visit. A similar plot will also be generated for raw values and % change from baseline.
- An individual plot presenting raw levels against study visit, paged by dose cohort and ambulatory status at baseline. A similar plot will also be generated for the change from baseline.

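### The all-assay rule in SAP 6.2 can discard a valid LC-MS or immunofluorescence result because a different assay failed, and it is narrower than the analysis set and estimand the SAP names.

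*SAP*

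**What the plan says.** SAP 6.2 opens the secondary analyses with an inclusion rule: "only sectioned tissue with results from each of the planned assays will be included in the summary". The reason it gives is "To limit possible variability by averaging or comparing results from different sections of a given muscle biopsy tissue". Section 6.2 does not list the planned assays. SAP 3.2.1.1 states that "Dystrophin and mini-dystrophin expression levels will be measured by LC-MS assay", and SAP 3.2.1.2 that "Dystrophin distribution will be evaluated by immunofluorescent staining using two antibodies". The count is thus two if immunofluorescence is one assay, or three if each antibody counts separately.

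The endpoints in SAP 6.2.1 and 6.2.2 are each defined within one assay and summarised as raw value, change and percent change from baseline. For both families, "The analyses will be performed using the Pharmacodynamic Analysis Set". SAP 4 defines that set as "All participants in the FAS who have baseline and at least" "one post-dose mini-dystrophin parameters of interest reported". The secondary estimand in SAP 2.3 refers, among eligible participants, to "those who receive a single IV infusion of fordadistrogene movaparvovec". Neither definition requires a complete set of assays.

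The visible text has no analysis of all available results, no count or listing of excluded tissue, and no comparison of included with excluded tissue.

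**The concern.** Followed exactly, the rule makes inclusion in an LC-MS summary depend on whether immunofluorescence worked on the same section, and the reverse. A missing stain does not make an LC-MS value less valid. The analysis set and the estimand point to one group of participants, and the rule may deliver a smaller one.

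The cohorts are 3 ambulatory low dose, 16 ambulatory high dose and 3 non-ambulatory high dose (SAP 2.5). In a cohort of three, one lost participant is a third of the evidence. Because 'planned assays' is undefined, two programmers could also build different datasets from the same text.

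The second possible consequence is selection. Protocol 1.4.3 describes fat replacing muscle as the disease advances. If poorer tissue fails assays more often and also shows lower expression, requiring every assay would tilt the summaries towards better muscle.

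**Working it through.** There is no plan figure to reproduce. The documents state no assay failure rate, no number of sections per biopsy and no power calculation (protocol 9.1; SAP 5.1). What follows is illustration under stated assumptions.

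**Inputs**
- Cohorts: 3 + 16 + 3 = 22 (SAP 2.5).
- Assays required, k: 2 or 3 (SAP 3.2.1.1, 3.2.1.2, 6.2).
- Chance p that an assay gives a result on a section: assumed 0.95, 0.90 or 0.80.
- Sections per biopsy, m: assumed 1, 2 or 3. SAP 6.2.2 averages over slides, so more than one is foreseen.
- Failures independent across assays, sections and visits: assumed.

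**Step 1. One section per biopsy, baseline plus one post-dose visit.** The share of pairs kept is p^2 on own-assay use and p^(2k) under the rule. Expected pairs out of 16 are in brackets.

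| p | own assay | rule, k=2 | rule, k=3 |
|---|---|---|---|
| 0.95 | 0.90 (14.4) | 0.81 (13.0) | 0.74 (11.8) |
| 0.90 | 0.81 (13.0) | 0.66 (10.5) | 0.53 (8.5) |
| 0.80 | 0.64 (10.2) | 0.41 (6.6) | 0.26 (4.2) |

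At p = 0.90, confidence intervals widen by about sqrt(0.810/0.656) = 1.11 (k=2) or sqrt(0.810/0.531) = 1.23 (k=3). A cohort of three keeps all three pairs with probability 0.810^3 = 0.53 on own-assay use, 0.656^3 = 0.28 (k=2) or 0.531^3 = 0.15 (k=3).

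**Step 2. Several sections per biopsy.** A biopsy is usable if at least one section is complete, so the pair rate is [1 - (1 - p^k)^m]^2. With p = 0.90 and k = 3, p^k = 0.729:
- m = 2: (1 - 0.271^2)^2 = 0.927^2 = 0.86, or 13.7 of 16; all three of three kept, 0.63.
- m = 3: (1 - 0.271^3)^2 = 0.980^2 = 0.96, or 15.4 of 16; all three of three kept, 0.89.

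Like for like, own-assay use gives (1 - 0.1^2)^2 = 0.98 and (1 - 0.1^3)^2 = 0.998. The gap due to the rule at k = 3 falls from 28 percentage points (m = 1) to about 12 (m = 2) and 4 (m = 3).

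**Step 3. Clustered failures.** If all assays on a section succeeded or failed together, p^k would become p and the rule would cost nothing relative to own-assay use. With one section and p = 0.90, positive dependence puts three-assay retention between 0.53 and 0.81.

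**Step 4. Direction.** A simulation of 2,000,000 draws at a single visit made assay success logistic in a standardised tissue-quality score (slope 0 or 1 per SD) and gave the outcome a correlation of 0, 0.3 or 0.5 with that score. With slope 0 or correlation 0, the mean shifts by no more than 0.003 SD. With slope 1 and correlation 0.3 to 0.5, over p = 0.95 to 0.80, the upward shift is 0.015 to 0.088 SD on own-assay use, 0.028 to 0.156 SD with two assays required and 0.039 to 0.210 SD with three. The part added by the rule is 0.013 to 0.068 SD (0.028 - 0.015; 0.156 - 0.088) for two assays and 0.024 to 0.122 SD (0.039 - 0.015; 0.210 - 0.088) for three. This concerns a level at one visit, not a change from baseline.

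**The case against.** The strongest defence is that the rule selects sections within a biopsy, not biopsies or participants. That stands. A reader might infer that one failed assay removes the whole biopsy pair, but the text does not say so: a biopsy with one complete section is still summarised. Steps 2 and 3 show how far this softens the loss.

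Second, the stated reason covers averaging as well as comparing, and SAP 6.2.2 does average percent positive fibers over slides within one assay. The rationale therefore has some bearing on a single-assay estimate. It still does not explain why a participant's only valid LC-MS result should be dropped for want of a stain.

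Third, SAP 6.2.1 and 6.2.2 name an analysis set without an all-assay condition, so inclusion of participants could be read as endpoint-specific, with 6.2 only choosing sections. That reading is possible, but 6.2 governs what enters the summary and nothing states which text prevails.

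Fourth, a reader might infer that the reported expression will be biased upward. The documents do not support that. They give no link between assay failure and tissue quality. LC-MS values below the limit of quantitation are imputed (SAP 5.3.3), so low expression alone does not exclude tissue. Fewer fibers is not the same as no result, because percent positive is calculated over the fibers present. The independence behind Step 1 also sits uneasily with the shared-quality mechanism behind Step 4, so the largest loss and the largest bias should not be quoted together.

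Finally, the SAP amendment history records the removal of an all-three-assay condition at version 3. A reader might infer that the sentence in 6.2 is a leftover. The history describes superseded text and settles nothing; the current sentence governs.

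**Conclusion.** The point holds in a limited form. The rule can discard valid single-assay results, is narrower than the analysis set and estimand the SAP names, and leaves its key terms undefined. The reason given supports matched sections for cross-assay comparison and, in part, for averaging. It does not support losing a participant's valid change from baseline.

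The size cannot be established from the documents. The 53% and 66% retention figures at 10% failure are one-section, independent-failure cases. More sections or clustered failures bring the loss down, possibly to very little. Any upward bias is conditional on two links that the documents do not show; own-assay use would reduce such a bias but not remove it. The endpoints are secondary and descriptive, with no formal hypothesis testing, so no error rate or power is affected. The change is still worth making, because it is cheap and two of the three cohorts have only three participants.

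**What to change.** In SAP 6.2, summarise each endpoint on all valid results from its own assay within the Pharmacodynamic Analysis Set, showing n per endpoint, cohort and visit. Keep the all-assay matched-section set for cross-assay comparisons or as a sensitivity analysis. State which assays are planned, in particular whether the two antibodies count as one or two, and what one unit of sectioned tissue is. Reconcile 6.2 with the analysis set in SAP 4 and the estimand in SAP 2.3. A listing of excluded tissue with reasons, and percent non-muscle tissue (already a variable in SAP 6.2.2) for included and excluded samples, would let a reader judge selection.

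The cost is SAP wording and some programming, with no new data collection. The downside is small: n may differ between assays, and some between-section variability is admitted.

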6.2.1. Mini-dystrophin/Dystrophin Expression by LC-MS

Endpoints:

- Mini-dystrophin levels, expressed as fmol/mg of total protein, measured by LC-MS assay, LEMPSSLMLEVPTHR (LEMP) peptide
- Total dystrophin levels, expressed as fmol/mg of total protein, measured by LC-MS assay, LLQVAVEDR (LLQV) peptide
- Total dystrophin levels, expressed as percent normal, measured by LC-MS assay, LLQVAVEDR (LLQV) peptide

The analyses listed below will be performed for each of the 3 endpoints. The method for handling results below the LLOQ is described in Section 5.3.3. The analyses will be performed using the Pharmacodynamic Analysis Set. Presentations will include:

- Raw values, change from baseline and % change from baseline will be summarized descriptively by dose cohort, ambulatory status at baseline, and study visit.
- A boxplot (for cohort(s) with over 3 participants, data points display only for cohort with ≤3 participants) presenting the distribution of the change from baseline against study visit. A similar plot will also be generated for raw values and % change from baseline.
- An individual plot presenting raw levels against study visit, paged by dose cohort and ambulatory status at baseline. A similar plot will also be generated for the change from baseline.

6.2.2. Mini-dystrophin/Dystrophin Distribution by Immunofluorescence

Endpoints:

- Percent of dystrophin and mini-dystrophin positive muscle fibers derived from the individual fiber MSD data, measured by immunofluorescence assay using DYSB antibody (IF DYSB)
- Percent of mini-dystrophin positive muscle fiber derived from the individual fibers MSD data, measured by immunofluorescence assay using mini-dystrophin specific antibody (IF mini-dys)

The analyses listed below will be performed for each of the 2 endpoints. The analyses will be performed using the Pharmacodynamic Analysis Set. Presentations will include:

• Raw values, change from baseline and % change from baseline will be summarized descriptively by dose cohort, ambulatory status at baseline, and study visit.

- A boxplot (for cohort(s) with over 3 participants, data points display only for cohort with ≤3 participants) presenting the distribution of the change from baseline against study visit. A similar plot will also be generated for raw values and % change from baseline.
- An individual plot presenting raw levels against study visit, paged by dose cohort and ambulatory status at baseline. A similar plot will also be generated for the change from baseline.

Determination of % positive fibers from the immunofluorescence assay (DYSB and minidystrophin specific antibody):

The primary variables include the percent of positive fibers, the total number of fibers, and the percent of non-muscle tissue in biopsy. The determination of percent positive fibers is summarized as follows:

- Biopsy samples in stained slides will be sent to an independent vendor for processing. The digital image of each slide is generated.
- An ROA is outlined by pathologists in a platform.
- Each fiber membrane is scanned using a scanner. The whole biopsy quantitation of dystrophin mean myofiber MSD is determined for each fiber within the ROA. These data are called the individual fiber MSD data.
- The fiber MSD value for each fiber in the ROA is compared to a positive fiber threshold value to determine the number of fibers exceeding the threshold value within the ROA for each slide. The percent of positive fibers is computed as the number of positive fibers divided by the total number of fibers for each slide.

For each participant, the individual baseline fiber MSD method will be used to determine the threshold for positive fibers to better characterize the individual change from baseline. The distribution of the individual fiber MSD data will be examined and plotted. The 95th percentile of the baseline fiber MSD distribution for each slide obtained prior to dosing will be computed. The maximum of the 95th percentiles obtained from the baseline distribution(s) will be used as the threshold for positive fibers. This individual threshold of staining density will be established for each participant such that at least 95% of fibers have a staining density below the threshold for each slide analyzed at baseline.

For the newly developed mini-DYS/Laminin Image Analysis assay, a global threshold for calculating the percentage of mini-dystrophin positive fibers will be established based on all baseline samples from the 19 ambulatory participants. The quantification of the immunofluorescence intensity level (MSD) associated with the individual muscle fibers will be used to calculate the 99th percentile of the overall fiber MSD distribution. The

[figure not shown]
corresponding fiber MSD threshold value will be determined. Any muscle fiber with an MSD value above this calculated threshold value will be considered as a positive fiber.

[figure not shown]
At each scheduled visit of muscle biopsy, the average of the percent of positive fibers obtained in each slide will be computed. This percent of positive fibers will be summarized by dose cohort and ambulatory status at baseline. Key fiber MSD distribution statistics including the mean and the median will be summarized. In addition, non-parametric Wilcoxon test will be used to examine the change in fiber MSD distributions.

[figure not shown]

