3.2. Secondary Endpoint(s)

3.2.1. Mini-dystrophin expression and distribution

- 1. Change from Baseline in percent normal dystrophin expression level in biceps brachii muscle biopsies at 2 (or 3) and 12 months post-treatment using an LC-MS assay
- 2. Change from Baseline in percent of dystrophin-positive muscle fibers in biceps brachii muscle biopsies at 2 (or 3) and 12 months post-treatment as assessed by immunofluorescence.

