5. GENERAL METHODOLOGY AND CONVENTIONS

5.1. Hypotheses and Decision Rules

There is no formal hypothesis testing in this study according to the original design of this FIH study. Because the study has a relatively small sample size and is not designed to have sufficient power to detect treatment differences, it is expected that hypothesis testing is not likely to reach statistical significance unless there is dramatic treatment effect. Nominal p-values will be presented. The 95% CI for the change from baseline in secondary (dystrophin expression/distribution)

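### The DYSB threshold is cut from each participant's own baseline slides, so the change in percent-positive fibres is not centred on zero under no effect if staining varies between biopsies

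*SAP*

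**What the plan says.** SAP 6.2.2 builds the DYSB cut-off from the participant's own pre-dose slides in two steps. First, "The 95th percentile of the baseline fiber MSD distribution for each slide obtained prior to dosing will be computed". Then, "The maximum of the 95th percentiles obtained from the baseline distribution(s) will be used as the threshold for positive fibers". The SAP states the consequence itself: "at least 95% of fibers have a staining density below the threshold for each slide analyzed at baseline".

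The same cut-off scores every later biopsy: "At each scheduled visit of muscle biopsy, the average of the percent of positive fibers obtained in each slide will be computed". For the summaries, "Raw values, change from baseline and % change from baseline will be summarized descriptively by dose cohort, ambulatory status at baseline, and study visit".

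SAP 3.2.1 lists the endpoint as "Change from Baseline in percent of dystrophin-positive muscle fibers in biceps brachii muscle biopsies at 2 (or 3) and 12 months", and SAP 2.1 lists the change in DYSB-positive fibres among the secondary estimands. SAP 5.1 announces an interval, "The 95% CI for the change from baseline in secondary (dystrophin expression/distribution"), together with nominal p-values and no formal hypothesis testing. SAP 5.2 and 6.2 make the interval a non-parametric bootstrap with 10,000 resamples.

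The mini-dystrophin-specific antibody is handled differently in the same section. It has one global threshold, the 99th percentile of the pooled baseline fibres of the 19 ambulatory participants.

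**The concern.** The baseline slides both set the cut-off and are scored against it, so no baseline slide can exceed 5%. A post-dose slide is scored against a cut-off that it did not help to set. A participant's change can therefore fall by at most 5 points but rise by up to 95.

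That asymmetry becomes an upward bias in the mean as soon as one biopsy stains somewhat brighter or dimmer than another for reasons unrelated to treatment. The SAP allows for such variation: 6.2 restricts which sections are used in order to limit variability, and taking a maximum over slides makes sense only if slides differ.

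The trial has no concurrent control, and SAP 2.3 makes the pre/post change the summary of treatment effect. Nothing inside the study cancels the bias. A reader who sees a 95% CI above zero for this change will take it as evidence of expression.

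**Working it through.** **Inputs from the documents.** Individual threshold at the maximum of the per-slide baseline 95th percentiles, and averaging over slides (SAP 6.2.2). Bootstrap 95% CI of the mean change (SAP 5.2). Cohort sizes of 16 ambulatory high dose, 3 ambulatory low dose and 3 non-ambulatory (SAP 2.5); 16 + 3 + 3 = 22.

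**Assumptions.** Fibre MSD on a slide is normal with SD 1. The biopsy-level shift has SD τ, in units of the fibre SD, and has the same distribution before and after dosing, so there is no treatment effect. The documents give no τ, so a range is shown. The interval is the percentile bootstrap, since SAP 5.2 does not name the type. All 16 participants have both biopsies.

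**The SAP's own figure.** In simulation under the stated rule, no baseline slide exceeded 5.0%. With one slide, baseline is 5% for everyone. With three slides (between-slide SD 0.2) it averages 3.6%, because the maximum raises the cut-off. The stated property holds.

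**Why the shift is upward.** With one slide the cut-off sits 1.645 SD above the baseline biopsy's centre.
- Post-dose biopsy brighter by 0.5 SD: 1 − Φ(1.145) = 12.6%, a change of +7.6 points.
- Post-dose biopsy dimmer by 0.5 SD: 1 − Φ(2.145) = 1.6%, a change of −3.4 points.

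These two equally likely cases average (7.6 − 3.4)/2 = +2.1 points.

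**Expected null change, one slide, many fibres.** The difference between two biopsy shifts has variance 2τ². Expected post-dose positivity is therefore 1 − Φ(1.645/√(1 + 2τ²)), and baseline is 5%. The last two columns are simulated at N=16 with the individual threshold.

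| τ | 1.645/√(1+2τ²) | post-dose % | null change (points) | bootstrap CI wholly above 0 | t-interval wholly above 0 |
|---|---|---|---|---|---|
| 0 | 1.645 | 5.0 | 0 | no excess | no excess |
| 0.1 | 1.629 | 5.2 | +0.2 | about 8% | about 5% |
| 0.25 | 1.551 | 6.05 | +1.05 | about 17% | about 9% |
| 0.5 | 1.343 | 8.96 | +3.96 | about 38% | about 17% |
| 1.0 | 0.950 | 17.1 | +12.1 | about 69% | about 43% |

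The nominal one-sided figure is 2.5%. With a finite number of fibres a trace of bias remains at τ = 0: +0.2 points with 500 fibres per slide and +0.03 with 3,000.

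**Pooled threshold, same null data.** One baseline 95th percentile applied to all slides gives a bias of about 0.05, 0.3 and 0.7–0.9 points at τ = 0.25, 0.5 and 1.0. CIs lie wholly above zero in about 5–6% of trials. What remains above 2.5% is small-sample under-coverage of the percentile bootstrap.

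**More slides do not remove the problem.** With three slides, CIs lie wholly above zero in 28% of trials at τ = 0.3 and 43% at τ = 0.5. Cutting the threshold from a second slide of the same baseline biopsy hardly helps: about 20% and 37–38%. What matters is that one biopsy's staining level fixes the participant's cut-off.

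**The N=3 cohorts.** With three values, 1/27 = 3.7% of bootstrap resamples consist of the smallest value three times. This exceeds 2.5%, so the lower limit is the smallest change. The CI lies above zero only if all three changes are positive, which has null probability (1/2)³ = 12.5%. Simulated rates for individual against pooled threshold are 12.8% and 12.9% (τ = 0.1), 12.4% and 12.4% (0.25), and 12.5% and 12.2% (1.0). The mean is still biased (about +4 points at τ = 0.5), but the CI error is that of bootstrapping three values.

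**The case against.** **No null is stated.** SAP 5.1 disclaims formal testing, 6.2.2 calls the summaries descriptive, and no dose decision uses this CI. This stands. A reader might infer that the plan contains a test that rejects wrongly; it does not. It does plan a CI and nominal p-values, and those will be read against zero.

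**The size rests on an unknown.** This also stands. A reader might infer that the CI excludes zero far too often whatever the staining variation. At τ of 0.1 or less the bias is 0.2 points or less and the excess is modest. Part of the exclusion rate belongs to the percentile bootstrap: a t-interval roughly halves it at τ = 0.25 and 0.5, but leaves 9% and 17%.

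**Small cohorts.** It is tempting to say that misleading CIs are worst in the low-dose and non-ambulatory cohorts. The calculation above does not support this. With N=3 the threshold rule makes no difference to the rate.

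**Other evidence exists.** SAP 6.2.2 also plans mean and median fibre MSD and a Wilcoxon comparison of MSD distributions, none of which needs a cut-off. Expression is also measured by LC-MS and by the mini-dystrophin-specific antibody, and neither carries this per-participant cap. So the point does not undermine the evidence of expression as a whole.

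**Pooling has a cost, and the precedent is not parallel.** The mini-dystrophin antibody has no endogenous target at baseline; DYSB does, and SAP 6.2.2 chose individual thresholds to describe individual change. Suppose 10% of fibres shift by 2 SD and τ = 0.1. The individual rule gives a mean change of 6.0 points. The pooled rule gives 5.1, 3.7 and 2.7 at assumed between-participant SDs of 0.5, 1.0 and 1.5. At τ = 0.25 and SD 1.5, CIs above zero fall from 100% to 76%. This stands, and it is why the pooled rule should be added beside the individual one and should not replace it.

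**Conclusion.** The concern holds in a conditional form. The ceiling of 5% at baseline, with none post-dose, follows from the SAP text without assumptions. The upward bias in the mean DYSB change needs only that staining varies between biopsies. Its size depends on a staining SD that the documents do not give: about +0.2 to +12 points at N=16 for SDs of 0.1 to 1.0 of the fibre SD. Over that range, percentile-bootstrap CIs lie wholly above zero in about 8% to 69% of null trials, against about 5–6% with a pooled threshold. These figures assume normal fibre staining and complete biopsy pairs.

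The consequence is an inflated change and a misleading nominal CI or p-value for one secondary endpoint, chiefly in the 16-participant cohort. A large true change would still show.

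**What to change.** In SAP 6.2.2, keep the individual DYSB threshold and make two additions.

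1. State that percent-positive at baseline is at most 5% by construction under this threshold, and that the CI or p-value for its change must not be read as evidence of expression against zero.
2. Report beside it the DYSB change from baseline and 95% CI with one pooled threshold: the 95th percentile of baseline fibre MSD over all participants with a baseline biopsy, each weighted equally, applied to every pre- and post-dose slide. Base any statement that the change exceeds zero on this analysis.

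The cost is SAP wording and one re-scoring of fibre-level data already held. The pooled cut-off does not adapt to a participant's own endogenous or revertant staining and can attenuate weak expression, so both versions should be shown together.
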